6.3 Withdrawal of patients from study

6.3.1 Screening failure

6.3.1.1 Prescreening failure

A patient whose tumor tissue is tested by IHC for mesothelin overexpression and whose result is not moderate (2+) and stronger (3+) mesothelin overexpression in at least 30% of the tumor cells, or who fails to meet any of the other eligibility criteria for prescreening, is regarded as a “prescreening failure”. These patients should not undergo any further screening procedures.

6.3.1.2 Full screening failure

A patient who passes the prescreening, including the mesothelin overexpression testing, but for any other reason (e.g., failure to satisfy the remaining selection criteria) terminates the study before enrollment is regarded as a “full screening failure”. See Section 11.1 for data to be collected for screening failures.

Re-starting the defined set of screening procedures to enable the “screening failure” patient’s participation at a later time point is not allowed – with the following exceptions:

- The patient had successfully passed the screening procedures, but could not start subsequent treatment on schedule.
- Initial screening occurred too early to complete the required washout period after prior therapy.
- The in- / exclusion criteria preventing the patient’s initial attempt to participate have been changed (via protocol amendment).
- Equivocal screening results require further testing for clarification even if, for logistical reasons, the further testing cannot be performed within the allocated time window (e.g. equivocal laboratory creatinine clearance requiring formal creatinine clearance measurement).
- Resolution of toxicity, now meeting all criteria

In any case, the investigator has to ensure that the repeated screening procedures do not expose the patient to an unjustifiable health risk. Also, for re-screening, the patient has to resign the main consent document (for the full study), even if it was not changed after the patient’s previous screening.

6.3.2 Withdrawal criteria

All patients who enter the study should complete all phases of the study unless they are screen failures or meet the criteria for withdrawal. Phases of the study include:

1. Prescreening
2. Full screening
3. Registration
4. Treatment
5. Safety follow-up
6. Active follow-up
7. Long-term follow-up

Study treatment discontinuation (i.e., discontinuation during the treatment period) does not constitute withdrawal from the study.

Every effort should be made to retain patients who discontinue the treatment period for any reason. These patients are to be encouraged to remain on the study for follow-up of primary, secondary and other objectives (i.e., continue in the safety follow-up, active follow-up and/or long-term follow-up periods).

Patients are expected to participate in the follow-up unless they explicitly object. Withdrawal of consent to treatment should be documented in the patient's medical record. If the patient does not wish to be followed up further, this additional consent withdrawal for follow up would have to be documented, too.

Withdrawal from study treatment, active follow-up and long-term follow-up

Patients withdrawn from **the study treatment** phase of the study should be followed for primary, secondary and other objectives (i.e. continue in the safety follow-up, active followup and/or long-term follow-up periods) (see Figure 2-1 for withdrawal criteria).

[figure not shown]
Figure 2-1 Withdrawal criteria

PATIENTS MUST BE WITHDRAWN FROM THE STUDY TREATMENT IF ANY OF THE FOLLOWING OCCURS:

- At their own request or at the request of their legally acceptable representative. At any time during the study and without giving reasons, a patient may decline to participate further. The patient will not suffer any disadvantage as a result.
- If, in the investigator's opinion, continuation of the study treatment would be harmful to the patient's well-being.
- At the specific request of the sponsor and in liaison with the investigator (e.g. obvious non-compliance, safety concerns).
- Confirmed radiological PD as per RECIST criteria.
- Clinical progression as assessed by investigator. Occurrence of unacceptable toxicity to anetumab ravtansine (see also Section 7.3.2).
- CTCAE Grade 4 hypersensitivity and acute infusion reaction.
- An adverse reaction deemed sufficiently serious to warrant discontinuation of treatment by the investigator or his designated associate(s).
- Development of a secondary malignancy.
- Patient starts treatment with any other anti-cancer therapy or any other prohibited medication as per Section 8.1.
- Positive serum β -HCG test consistent with pregnancy. Pregnancy should be reported along the same timelines as an SAE.
- Use of illicit drugs or other substances that may, in the opinion of the investigator or his designated associate(s), have a reasonable chance of contributing to toxicity or otherwise confound the results.
- Development of any intercurrent illness or situation which may, in the judgment of the investigator, affect assessments of clinical status and study endpoints to a relevant degree.
- Lost to follow-up.
- Death.

Patients must be withdrawn from **treatment with anetumab ravtansine** if any of the following occurs:

- CTCAE Grade 4 non-hematological AE and Bayer Grade 4 corneal toxicity (see Table 2-6) (except at the investigator's discretion in case of certain Grade 4 abnormality of laboratory assessments, such as abnormal laboratory assessments without corresponding clinical symptoms, or abnormal laboratory assessments that can be easily clinically managed).
- If any type of TEAE requiring dose modification does not resolve to Grade ≤ 1 (or Hb ≥ 8 g/dL in case of anemia) within 6 weeks after the last dose of anetumab ravtansine.
- Delay in anetumab ravtansine administration of 3 weeks (max. 6 weeks between 2 infusions of study drug).
- TEAE requiring dose reduction when already at the 4.5 mg/kg Q3W dose level (minimum dose).
- More than 2 dose reductions required due to a TEAE.

AE = Adverse event; β -HCG = β subunit of human chorionic gonadotropin; CTCAE = Common Terminology Criteria for Adverse Events; Hb = Hemoglobin; RECIST = Response Evaluation Criteria in Solid Tumors; PD = Progressive disease; Q3W = Every 3 weeks; SAE = Serious adverse event; TEAE = Treatment-emergent adverse event

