- Platelet count $\geq 75,000/\text{mm}^3$, without platelet transfusion within 3 weeks before the start of study treatment (see Section 8.1).
- Hemoglobin (Hb) $\geq 8 \text{ g/dL}$,

Note: Patients receiving chronic low-dose erythropoietin for chronic renal failure are allowed provided no dose adjustment is undertaken within 6 weeks before signing consent for full study and until safety follow-up visit and provided that they fulfill conditions of eligibility criteria (see also exclusion criterion number 18).

- Absolute neutrophil count (ANC) $\geq 1000/\text{mm}^3$

9. Left ventricular ejection fraction (LVEF) $\geq 50\%$ or the lower limit of normal (LLN) according to local institution ranges of normality.

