- c Febrile neutropenia is defined as ANC < 1000/mm³ and fever (a single body temperature reading of > 38.3°C [101°F] or a sustained body temperature of ≥ 38°C [100.4°F] for more than 1 hour).

Clinical Study Protocol

19-September-2018

BAY 94-9343 (Anetumab in Pancreatic Cancer)
Version 4.0

Page: 28 of 77

Table 2-4: Dose adjustments in response to pre-infusion values

Absolute neutrophil count (/mm ³)	Platelets (/mm ³)	Hemoglobin (g/dL)	Treat	Anetumab ravtansine dose adjustment
≥ 1,000	and	≥ 75,000	Treat on time	Adjust dose by nadir ^a counts in previous cycle per investigator's discretion
< 1,000	and	< 75,000	Delay until ANC ≥ 1.0 and platelets ≥ 75,000 ^b	Decrease by 1 dose level ^c
		< 8	Delay until Hb ≥ 8 ^b	Re-start at the same dose or decrease by 1 dose level ^c (at investigator's discretion)

ANC = Absolute neutrophil count; C = Cycle; CBC = Complete blood count; D = Day; Hb = Hemoglobin; Q3W = Every 3 weeks; TEAE = Treatment-emergent adverse event

- a Site visits and blood test for CBC (and biochemistry) on D8 and D15 will be performed on C1, C2 and C3 only. From Cycle 4 onwards, visits and procedures on D8 and D15 are no longer required.
- b Treatment will be discontinued if the TEAE fails to resolve to Grade ≤ 1 (or Hb ≥ 9 g/dL in case of anemia) within 6 weeks after the last dose of anetumab ravtansine.
- c Dose reduction by 1 dose level translates to a change from 6.5 mg/kg Q3W to 5.5 mg/kg Q3W, or from 5.5 mg/kg Q3W to 4.5 mg/kg Q3W. Not more than 2 dose reductions from the starting dose level are permitted.

7.3.2.2 Non-hematological toxicities**Non-hematological toxicities requiring dose or infusion modification**

- CTCAE Grade 2 or Grade 3 anetumab ravtansine infusion reaction or other CTCAE Grade 2 or Grade 3 hypersensitivity events (see Section 7.3.2.1.3)
- AST and/or ALT increase > 5.0 x ULN (CTCAE Grade ≥ 3)
- AST and/or ALT increase > 3.0 x ULN (CTCAE Grade ≥ 2) with concomitant increase in total bilirubin > 1.5 x ULN (CTCAE Grade ≥ 2)
- Total bilirubin > 3.0 x ULN (CTCAE Grade ≥ 3)
- Bayer Grade ≥ 3 corneal toxicity (see below and **Table 2-6**)
- Any other Grade ≥ 3 non-hematological toxicity that, in the investigator's opinion, warrants treatment modification (see **Table 2-5**), **excluding** the following:
 - Nausea, vomiting, or diarrhea if manageable with anti-emetics or antidiarrheals within 7 days
 - Hair loss
 - Fatigue lasting ≤ 72 h

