 - Certain asymptomatic laboratory assessments without a clear clinical correlate, if the investigator determines that this TEAE would not require treatment modification
- Any other toxicity irrespective of the type or severity that represents a clinically significant risk to patient in the investigator's opinion.

Dose modifications for non-hematological toxicity

If treatment modification is required due to a **non-hematological TEAE** as listed above, other than corneal toxicity and infusion reaction/hypersensitivity events, and the continuation of treatment is appropriate, the anetumab ravtansine dose will be either reduced or maintained as is at investigator's discretion (see **Table 2-5**).

Table 2-5: Dose adjustments in response to non-hematologic toxicities

CTCAE v4.03 grade	Anetumab ravtansine dose delay / interruption	Anetumab ravtansine dose modification
Grade 1 – 2 ^a	Treat on time	No change required (at investigator's discretion)
Grade 3	1 st appearance: Delay/Interruption until Grade ≤ 2 ^b	Re-start at the same dose or decrease by 1 dose level ^c (at investigator's discretion)
	2 nd appearance: Delay/Interruption until Grade ≤ 2 ^b	Decrease by 1 more dose level ^c
	3 rd appearance: Permanently discontinue	
Grade 4	Permanently discontinue	

ALT = Alanine aminotransferase; AST = Aspartate aminotransferase; CTCAE = Common Terminology Criteria for Adverse Events; Q3W = Every 3 weeks; TEAE = Treatment-emergent adverse event

- a AST and/or ALT increase of CTCAE Grade 2 with concomitant increase in total bilirubin of CTCAE Grade 2 will be treated as a CTCAE Grade 3 event.
- b Treatment will be discontinued if the TEAE fails to resolve to Grade \leq 1 within 6 weeks after the last dose of anetumab ravtansine.
- c Dose reduction by 1 dose level translates to a change from 6.5 mg/kg Q3W to 5.5 mg/kg Q3W, or from 5.5 mg/kg Q3W to 4.5 mg/kg Q3W. Not more than 2 dose reductions from the starting dose level are permitted.

The anetumab ravtansine dose reduction due to non-hematological TEAE will be done as described below:

- If the patient experienced a TEAE requiring dose reduction at the 6.5 mg/kg Q3W dose level, the subsequent anetumab ravtansine dose should be reduced to 5.5 mg/kg Q3W.
- If the patient experienced a TEAE requiring dose reduction at the 5.5 mg/kg Q3W dose level, the subsequent anetumab ravtansine dose should be reduced to 4.5 mg/kg Q3W.

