7.3.2.4 Continuation of treatment with anetumab ravtansine

Treatment with anetumab ravtansine could be re-started at the appropriate dose if the TEAE requiring dose modification has resolved to Grade < 2 within 6 weeks after the last dose of anetumab ravtansine.

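### Re-start and recovery limits conflict for Grade 3 non-hematologic events, anemia and corneal events, so sites can dose or hold the same patient differently

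*Combined protocol and SAP*

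**What the plan says.** **Withdrawal rule.** Figure 2-1 in Section 6.3.2 withdraws drug "If any type of TEAE requiring dose modification does not resolve to Grade" ≤ 1, with the alternative of Hb ≥ "8 g/dL in case of anemia) within 6 weeks after the last dose of anetumab ravtansine". The bullet covers every type of TEAE that requires dose modification. The next bullet withdraws drug after a 3-week delay, with at most 6 weeks between infusions.

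**Non-hematologic Grade 3 events.** The body of Table 2-5 (Section 7.3.2.2) says, for the first and second occurrence, "appearance: Delay/Interruption until Grade" ≤ 2. Note b to the same table says "Treatment will be discontinued if the TEAE fails to resolve to Grade" ≤ 1 within six weeks of the last dose. Section 7.3.2.4 says that drug could be re-started "if the TEAE requiring dose modification has resolved to Grade" < 2 within the same six weeks.

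**Anemia.** The hemoglobin row of Table 2-4 says "Delay until Hb" ≥ 8. Note b, attached to that cell, discontinues unless Hb reaches ≥ "9 g/dL in case of anemia" within six weeks. Entry (Section 6.1.2, criterion 8) also requires Hb ≥ 8 g/dL.

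**Corneal events.** Section 7.3.2.3 makes related corneal morphology changes events that require modification and sends them to Table 2-6. For Grade 3, item 1 of that table lowers the dose. Item 2 re-starts at the original dose if the first event falls to Grade ≤ 2 within 3 weeks. Item 3 continues at level -2 (or -3) if it does not.

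**Related rules.** The dose levels in Section 7.3.2 end at -2 (4.5 mg/kg). The close of Section 7.3.2.2 forbids raising a patient's dose again after any reduction. Section 7.3.2.5 refers to 6.3.1.2 for the withdrawal criteria, but 6.3.1.2 deals with full screening failure.

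**The concern.** A site that follows the protocol to the letter can reach opposite dosing decisions for the same patient, depending on which line it reads. Section 13.4 requires strict adherence and does not let investigators alter procedures, and nothing in the plan says which text governs re-start.

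The events are expected. Section 3.1 names Grade 3 AST/ALT increase as the only dose-limiting toxicity at 6.5 mg/kg and describes a high incidence of corneal toxicity at that dose.

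At stake are patient safety and a secondary objective, toxicity. Section 10.2.2.2 will report how many patients discontinue, reduce or interrupt drug because of an AE. With 2-3 centers, those counts would partly reflect local reading of the rules.

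**Working it through.** The plan has no figure to reproduce here. The check sets the limits side by side and runs one test patient through each.

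| Event | Table body | Table note b (6 weeks) | Figure 2-1 (6 weeks) | 7.3.2.4 (re-start) |
|---|---|---|---|---|
| Grade 3 non-hematologic (Table 2-5) | Grade ≤ 2 | Grade ≤ 1 | Grade ≤ 1 | Grade < 2 |
| Anemia (Table 2-4) | Hb ≥ 8 | Hb ≥ 9 | Hb ≥ 8 | Grade < 2, no Hb alternative |
| Corneal Grade 3 (Table 2-6) | Grade ≤ 2 | none | Grade ≤ 1, no exception | Grade < 2, no exception |

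Delay cap: 3-week cycle + 3-week delay = 6 weeks between infusions.

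**Patient A, AST.** Section 7.3.2.2 puts AST above 5.0 x ULN at Grade 3 and above 3.0 x ULN at Grade 2. Related AST of 6 x ULN falls to 4 x ULN, with bilirubin no higher than 1.5 x ULN so that note a to Table 2-5 does not apply.
- The Table 2-5 body permits the dose. Section 7.3.2.4 does not.
- If AST is still 4 x ULN at six weeks and no dose has been given, note b, Figure 2-1 and the delay cap all end treatment, so there is no divergence about stopping.
- If the patient was re-dosed at Grade 2, that infusion can be read as the new last dose. Note b and Figure 2-1 then act as a later backstop and do not conflict with the body. The conflict that remains is between the body and 7.3.2.4.

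**Patient B, Hb 8.5 g/dL.** The limits differ over 8 to < 9 g/dL.
- Before week 6, the Table 2-4 body allows re-start, and re-dosing may reset the clock in note b.
- At week 6 with no dose given, the body and Figure 2-1 allow an infusion that day, while note b discontinues. Past week 6 the delay cap ends treatment in any case.
- The operational window is therefore narrow: an infusion at week 6 itself, or a site that does not reset the clock on re-dosing. The two printed limits for the same rule still cannot both be right.

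**Patient C, corneal Grade 3 improved to Grade 2 within 3 weeks.**
- Table 2-6 re-starts. Section 7.3.2.4 does not.
- Figure 2-1 makes no exception, but if dosing continues under Table 2-6 its six-week clock may reset with each infusion. The firm conflict is with 7.3.2.4.
- If item 1 has already taken the dose from 6.5 to 5.5 mg/kg, item 2 returns it to 6.5, which the bar on re-escalation forbids.
- Item 3 allows level -3. No such level exists, and Figure 2-1 withdraws a patient who needs a reduction below 4.5 mg/kg.

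**Size.** The only corneal rate in the documents is 12/32 = 37.5% (Section 3.1), from the ovarian cancer and mesothelioma cohorts at 6.5 mg/kg. It counts corneal toxicity without Bayer grades. The share reaching Grade 3 and then improving to Grade 2 is not given, nor is any rate for the AST or hemoglobin zones.

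**The case against.** Four points on the other side have weight.

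- **The delay cap.** It settles many cases before the recovery limits matter. A reader might infer that a patient undosed at six weeks with AST at 4 x ULN is stopped under one rule and treated under another. The documents do not support that, because every rule stops drug there. The cap also narrows the hemoglobin conflict, as shown for Patient B.
- **The wording of 7.3.2.4.** It says drug could be re-started if the event has fallen below Grade 2; it does not say only if. A reader might infer a flat prohibition at Grade 2, but a permissive reading is possible. The natural reading is still a condition for re-start, since the sentence would otherwise set no limit.
- **Precedence.** Section 7.3.2.5 sends permanent discontinuation to the withdrawal criteria. The section number is wrong but the target is clear, and this favors Figure 2-1 (Hb ≥ 8) over a table footnote. It does not settle re-start.
- **A separate corneal scheme.** Section 7.3.2.2 takes corneal events out of the Table 2-5 adjustments, and 7.3.2.3 gives them their own table. A specific table would often be taken to override a general sentence. The plan does not say so, and Figure 2-1 refers to Table 2-6 for Grade 4 events but not in its recovery bullet.

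A reader might also take 12 of 32, scaled to 30 patients (0.375 x 30 = 11.25), as the number affected. It is not: the figure is ungraded and comes from other tumor types.

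**Conclusion.** The conflicts are in the current text and should be corrected. The firm ones are the Table 2-5 body against 7.3.2.4 at Grade 2, 9 against 8 g/dL for one discontinuation rule, and Table 2-6 against 7.3.2.4 at corneal Grade 2. The -3 dose level and the return to original dose in Table 2-6 are further errors in the same rules; the second arises only when the dose has already been reduced. Note b to Table 2-5 and the recovery bullet of Figure 2-1 can be read as a later backstop, so they are not counted as firm conflicts with the table bodies.

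The conclusion assumes that 7.3.2.4 is meant as a condition for re-start. The hemoglobin mismatch stands as text, with a narrow practical window. The number of patients affected cannot be derived.

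The consequence is for dosing safety and the descriptive counts of interruptions, reductions and discontinuations. A reader might infer harm to the primary test, but the Simon figures do not depend on these limits, and Section 9.2.5.2 continues tumor assessment after drug is stopped for reasons other than confirmed radiological progression.

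**What to change.** 1. **Hemoglobin.** In Table 2-4 note b, change Hb ≥ 9 to Hb ≥ 8 g/dL, and add the Hb ≥ 8 alternative to 7.3.2.4.
2. **Non-hematologic re-start.** Use one grade in the Table 2-5 body and 7.3.2.4. The default is Grade ≤ 1, which matches note b and Figure 2-1. The sponsor should decide whether to add a return-to-baseline alternative, because entry allows Grade 2 neuropathy (exclusion 21) and ALT/AST up to 5 x ULN with liver involvement (Section 6.1.2). Such patients could return to their own baseline and still not qualify.
3. **Corneal events.** State in 7.3.2.4 and Figure 2-1 that corneal events follow Table 2-6 for the recovery grade, or change Table 2-6 to Grade ≤ 1. The choice is the sponsor's. Keep the 6-week maximum between infusions either way.
4. **Table 2-6.** Delete the -3 level, and reword item 2 so that a dose already reduced is not raised again.
5. **Cross-reference.** In 7.3.2.5, change 6.3.1.2 to 6.3.2.

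The cost is amendment wording, with no new visits, tests or patients. There are two downsides. Some patients who would now re-start at Grade 2 would be held longer, by at most 6 - 3 = 3 weeks, and a few may reach the delay cap and stop drug. With the corneal exception, a corneal event still at Grade 2 at six weeks would no longer by itself force withdrawal.

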6.3.3. Lost to follow-up patients

When a patient is lost to follow-up at any stage of the study, the site should try to contact the patient, the patient's relatives, or another doctor treating the patient, unless prohibited by local regulations. All attempts to contact the patient or relatives should be documented.

6.3.4 General withdrawal procedures

In all cases, the reason for withdrawal must be recorded in the CRF and in the patient's medical records.

The patient may object to the generation and processing of post-withdrawal data as specified below.

Details for the premature termination of the study as a whole (or components thereof) are provided in Section 12.

6.3.5 Replacement

No replacement of patients will be allowed during this study.

6.4 Patient identification

After a patient has signed the prescreening consent form, the coordinating center will provide a patient identification number to be entered into OnCore (Clinical Trials Management System).

7. Treatment(s)

7.1 Treatments to be administered

All patients who meet the entry criteria will receive the test drug anetumab ravtansine, considered to be an IMP: anetumab ravtansine 6.5 mg/kg IV Q3W

7.2 Identity of study treatment

All study drugs will be labeled according to the requirements of local law and legislation.

Anetumab ravtansine will receive study-specific labeling and will be provided by the sponsor.

For all study drugs, a system of numbering in accordance with all requirements of GMP will be used, ensuring that each dose of study drug can be traced back to the respective bulk batch of the ingredients. Lists linking all numbering levels will be maintained by Bayer's clinical supplies quality assurance (QA) group.

A complete record of batch numbers and expiry dates of all study treatment as well as the labels will be maintained in the sponsor's study file.

7.2.1 Test drug - anetumab ravtansine

Anetumab ravtansine is an ADC consisting of a fully human IgG1 antibody (MF T, BAY 861903) directed at the mesothelin antigen and conjugated to a synthetic maytansine derivative as toxophore (DM4, BAY 100-6640) through a reducible disulfide linker (SPDB linker).

The details of the investigational drug are given in **Table 2-1**.

Table 2-1 Identity of anetumab ravtansine

Chemical name	Mesothelin antibody-drug conjugate: Immunoglobulin G1, anti-(human mesothelin) human monoclonal MF-T-IgG1 heavy chain, disulfide with human monoclonal MF-T-IgG1 κ -chain, dimer, triamide with N2'-[4-[(3-carboxypropyl) dithio]-4-methyl-1oxopentyl]-N2'-deacetylmytansine
Substance code number(s)	BAY 94-9343
Appearance	
Freeze-dried drug product	White to off-white lyophilized cake or powder
Reconstituted solution	Clear or slightly opalescent solution
Formulation	Freeze-dried product in a 30 mL injection vial, containing 5 mg/mL of active ingredient after reconstitution
Composition	Anetumab ravtansine / BAY 94-9343 / L-histidine / glycine / sucrose / polysorbate 80 / 1 N HCl
Type of packaging and content	30 mL injection vial

IgG1 = Immunoglobulin G subclass 1; N HCl = Normal hydrochloric acid

The drug product is available as a lyophilizate. Each vial contains 62.5 mg of anetumab ravtansine; the amount available for administration, based on retractable volume of reconstituted solution, is 60 mg of anetumab ravtansine. It should be reconstituted in water for injection and diluted in 0.9% sodium chloride solution (normal saline) prior to administration as IV infusion.

The drug product is to be stored at 2°C to 8°C (36°F to 46°F).

